June 12, 2023

Ifaa Effectiveness Evaluation on Food Security and Nutrition

NCT05825716

Clinicaltrials.gov NCT05825716

JHSPH IRB Research Plan for New Data Collection

IRB Version: 11May2023

For new data collection, new data collection plus secondary data analysis, biospecimen repositories, and data coordinating center protocols.

DO NOT DELETE ANY QUESTIONS FROM THIS TEMPLATE

PI Name: [name]

Study Title: Ifaa Effectiveness

IRB No.: 23765

PI Version No. / Date: Version 4, June 12, 2023

I. Aims of the Study:

The Ifaa Project is a USAID-funded Resilience and Food Security Activity (RFSA) that is being implemented by Catholic Relief Services (CRS) and partners in the East Hararghe Zone of the Oromia Region in Ethiopia. Ifaa targets households that are participating in Productive Safety Net Programme (PSNP) which is a social protection program administered by the Government of Ethiopia that provides food and cash assistance to vulnerable households. The Ifaa Project will deliver multi-sectoral programming in 241 kebeles (sub-districts) in nine woredas (districts) of East Hararghe Zone, however, intervention packages vary by location. The proposed effectiveness evaluation will quantify the impacts of three different intervention packages in terms of key project indicators in the areas of household food security, diet, and child nutrition.

II. Background and Rationale:

Food insecurity and child undernutrition are persistent challenges in Ethiopia. In early 2023, over 22 million Ethiopians are food insecure as a result of drought, conflict and rising food prices and the situation is expected to worsen.ⁱ Prevalence of chronic malnutrition (stunting) is estimated at 37% and prevalence of acute malnutrition (wasting) is 7% among children less than five years of age. Only 14% of children have adequate dietary diversity and 11% meet the criteria for having a minimally acceptable diet.ⁱⁱ

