A subset of kebeles (n=70) was randomly allocated to Ifaa Basic and Ifaa Enhanced Packages as part of a cross-RFSA learning activity (USAID is supporting similar projects in other regions of Ethiopia) that is supported by the funder, USAID Bureau of Humanitarian Affairs. This effectiveness evaluation leverages this randomization to compare the two intervention packages. Additionally, 50% of kebeles were selected for livelihoods interventions, which occur in both Basic and Enhanced kebeles; livelihoods kebeles were selected based on criteria developed by CRS, but assignment to the enhanced vs basic package was random. Finally, approximately half of Ifaa Project kebeles are 'the free zone' where there is flexibility in intervention packages of the course of the project.¹ The distribution of the three Ifaa intervention packages that will compare in the proposed effectiveness evaluation is presented in **Table 2** below.

Table 2: Ifaa Intervention Allocation by Administrative Area

| Woredas/Districts Intervention Package | Study Eligible Kebeles/Sub-Districts* | | |
|---|---------------------------------------|---|--|
| | Ifaa Basic (n=25) | Ifaa Enhanced (n=34) | Ifaa Enhanced + Livelihoods (n=35) |
| Babile | Gemechu Ifa Jalale | Lekolo Shek husen Tofiq Tuluhoro | Erer guda Gambela Ibada gemechu Nejata gemechis |
| Chinaksan | Chelchale Kobobika | Biftuu Waree Gela | Amola Baduelemo |

¹ These kebeles were not considered in the sampling frame because of the high risk of contamination.

| | Migira | Kaleroga | Dawe kora |
|-------------|---|--|---|
| | Tiro gudoo Wachuhulet | Orda sost Tirosendare | Dembesele Kocher Merer Mudi dawe |
| Deder | Burka Berekha Mumicha Nedi gelansedi | Gegewisa Haremlemekuni Huffe Kura deder Lemen welteha | Burka Geba Cheka gemechu Chela Negeya Golu Oda kebena Welteha gudina |
| Fedis | Bareda Bedatu | Bid Borra Efitu dada Negaya bobasa Risiki | Ido Baaso Kerensa lencho Umer kule |
| Gursum | Ebsa Hariro Misira Saqabadii | Berite Gara wadaja Gefire guda Goro siyo Kebso Negeya | Awdal Day feres Harashi Kasa oromiya Oda oromiya |
| Jarso | Aneno mite Burka mete Debub debelo | Amen Epa jalela Gidiya licha Oda muda | Afgug Chala Gara abdula |
| Melka Belo | Fule negeya Haka mulisi Tokuma bilisumu | Bifitu negeya Daba kenisa Mulisa hakwa Tokuman kane | Chefe Jeneta Dire Qufa Welikituma bilusuma |
| Midega Tola | Ibiro musa Terkafeta | Kerensa Mukura | Bilisuma Biyo waraba Lencha Roba |

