As noted in Figure 1, the study includes three of the possible four Ifaa intervention combinations. Characterizing the impact of livelihoods programming without the Ifaa enhanced intervention was not considered a priority.

Figure 2. Study Flow Diagram

A longitudinal cohort design will be used to compare the effectiveness of three Ifaa intervention packages among PSNP beneficiaries: 1) the Ifaa basic package; 2) enhanced package without livelihoods; and 3) enhanced package with livelihoods. Under this approach, the enrolled households will have either a pregnant woman or children <36 months of age. Households will be followed over a two-year period, with the baseline and endline survey conducted at a similar time

³ Community led complementary feeding sessions (CCFLS) is a six month program targeted at children at risk of acute malnutrition or recently discharged from a malnutrition treatment program. It includes caregiver training on child feeding practices and growth monitoring and is a six month intervention, with intensive services/training in the first month and follow up monitoring.

period in the calendar year to avoid seasonal changes in food security. The magnitude of change in key indicators over time will be assessed for each group; if needed, adjusted models will be used to account for baseline differences between groups. Outcome measures of focus are aligned with Ifaa indicators and include measures of household food consumption and child diet. To ensure adequate geographic coverage, a **stratified sampling design** will be used as follows:

- (1) **Kebele Selection.** Two kebeles per intervention arm will be purposively selected in each of the nine woredas with the aims of 1) of maximizing geographic similarity in terms of agro-ecological zone (lowland, midland, highland) and remoteness; and 2) ensuring sufficiently large beneficiary population is available for sampling purposes. In the case of smaller kebeles where it appears unfeasible to attain three clusters, the sample may be distributed across additional kebeles within the woreda.⁴

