The outcome variables of focus at the household level will be measures of food security, including 1) [Food Consumption Score](#), 2) [Household Hunger Scale](#), and 3) [Coping Strategies Index](#). At the individual level, outcome variables of focus will include 1) [Infant and Young Child Feeding Indicators](#) (in particular achievement of minimum dietary diversity); and 2) prevalence of stunting and wasting, in accordance with the [World Health Organization Child Growth Standards](#). Background information on individual (e.g. literacy, age, pregnancy status) and household characteristics (e.g. size, residence location) will also be collected so that these can be controlled for or used for disaggregation in data analysis. All outcomes will be analyzed as continuous variables and as categorical variables based on pre-determined thresholds.

A descriptive analysis of household sociodemographic characteristics and outcome measures will be performed. Continuous variables will be presented as mean (SD) and categorical variables as n (%). ANOVA tests will be conducted for baseline characteristics and primary and secondary outcomes to examine the comparability between the three and intervention groups; individual/household characteristics with significant differences between groups at baseline will be controlled for in models that estimate the effect of the interventions.

The program effect on expected primary outcome measures will be estimated using mixed-effect linear regression analysis for continuous outcomes and Generalized Estimation Equation (GEE) model for binary outcomes. In the mixed-effects models, the random effect component included indicators to control for clustering at school levels. The fixed component included the intervention group (intervention vs. control), time and an interaction term for group and time. The GEE models will be used to examine binary outcomes with longitudinal data from both enrollment and endline. These models will estimate the change in a binary outcome among members of a given intervention group from enrollment to endline, compared to the change in the same outcome in the control. The GEE models also included an interaction term between the intervention group and time (baseline/endline).

5. **Answer the following if they are relevant to your study design:**

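### The mixed model for continuous outcomes has a two-level group term in a three-package study, and no contrast between the two Enhanced packages is specified

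*Combined protocol and SAP*

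**What the plan says.** - **Aim (Section I).** The evaluation is to "quantify the impacts of three different intervention packages".
- **Design (Section III.A).** "A longitudinal cohort design will be used to compare the effectiveness of three Ifaa intervention packages among PSNP beneficiaries". The packages are listed as "1) the Ifaa basic package; 2) enhanced package without livelihoods; and 3) enhanced package with livelihoods". The same section adds: "The magnitude of change in key indicators over time will be assessed for each group". Figure 1 shows that Basic with livelihoods is not a study arm.
- **Continuous outcomes (Section V.C, item 3).** These go to a mixed-effects linear model: "The fixed component included the intervention group (intervention vs. control), time and an interaction term for group and time".
- **Binary outcomes (same item).** These go to GEE: "These models will estimate the change in a binary outcome among members of a given intervention group from enrollment to endline". The yardstick is the control group's own change. A group-by-time interaction is mentioned, but the number of group levels is not.
- **Scale (same item).** Every outcome is to be analysed both as a continuous variable and in categories, so the Food Consumption Score passes through both models.
- **Assignment.** Section II says "livelihoods kebeles were selected based on criteria developed by CRS, but assignment to the enhanced vs basic package was random". Section III.A says that half of the Basic kebeles receive livelihoods at random. Section V.C, item 5.A says that sites are allocated purposively to all three packages, which it labels as a comparison and interventions 1 and 2.

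**The concern.** A term with the two levels intervention and control has one group-by-time coefficient. In a three-package study, an analyst who follows that sentence must put Enhanced and Enhanced + Livelihoods together. The result answers whether any Enhanced package differs from Basic. It does not give the effect of each package, which is the stated aim.

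The missing contrast matters as well. Because Basic with livelihoods is not studied, what livelihoods add can be learned only by comparing Enhanced + Livelihoods with Enhanced. Those arms hold 2 x 1,080 = 2,160 of the 3,240 planned households (2,160 x 0.8 = 1,728 after the assumed 20% loss), yet the plan never names that comparison. If the text stays open, pooled or separate effects could be chosen after the endline data are seen.

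**Working it through.** **1. The plan's own sample size.** Inputs from Section III.B: alpha 0.05 (two-sided assumed), power 80%, design effect 1.5, loss 20%, change of 8 points. The formula is the two-proportion one with pooled null variance, times 1.5, times 1.2 for loss:

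n = [1.96 x sqrt(2 x pbar x (1 - pbar)) + 0.842 x sqrt(p1(1 - p1) + p2(1 - p2))]^2 / (p1 - p2)^2

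- 34% to 26%: n = 514; 514 x 1.5 x 1.2 = 925 (stated 915).
- 48% to 40%: n = 604; 604 x 1.5 x 1.2 = 1,087 (stated 1,070). This row is matched to the 48% baseline by calculation, because the table is broken.

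Eight of the nine rows in Table 3 agree within 3% this way. The exception is 609, for which this formula gives 581. The sizing is thus per group for three groups. The section describes it as based on within-group change, and also claims that differences of at least 8% between groups can be detected.

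**2. What the literal model estimates.** Let d_E and d_EL be the effects on change, relative to Basic, of Enhanced and Enhanced + Livelihoods on a continuous score. With equal numbers in both arms at both visits, the pooled coefficient is (d_E + d_EL) / 2.

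- d_E = -4, d_EL = -12: pooled -8.
- d_E = -8, d_EL = -8: pooled -8.

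The livelihoods increment, d_EL - d_E, is -8 in the first case and 0 in the second. The model cannot tell them apart. These values are illustrative.

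**3. Precision.** With n per arm, equal variance of change and equal clustering:

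SE pooled / SE pairwise = sqrt(1/n + 1/(2n)) / sqrt(2/n) = sqrt(1.5/2) = 0.866

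The averaged answer therefore has a standard error about 13% smaller than that of a contrast between two packages.

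**4. Which contrasts the text supplies.**

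| Contrast in change | Mixed model, as written | GEE, as written |
|---|---|---|
| Enhanced vs Basic | only within the average | allowed |
| Enhanced + Livelihoods vs Basic | only within the average | allowed |
| Enhanced + Livelihoods vs Enhanced | absent | not specified |

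**5. What separate contrasts cost.** The documents give no standard deviation for the continuous scores, so the binary outcomes serve as a guide. Effective n per arm = 1,080 x 0.8 / 1.5 = 576. The reference arm is assumed to stay at its baseline value, and the other arm differs by 8 points. The endline columns use a pooled-variance normal approximation. For the group-by-time contrast, power = Phi(0.08 / SE - 1.96). Each arm contributes a variance of change of (v0 + v1 - 2 x rho x sqrt(v0 x v1)) / 576, where v0 and v1 are p(1 - p) at baseline and endline. For the pooled column, the variance of the changed arm is halved. The baseline-endline correlation rho is not in the documents; 0 to 0.6 is assumed.

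| Reference to comparison | Endline, alpha 0.05 | Endline, alpha 0.05/3 | Group-by-time, pairwise | Group-by-time, pooled |
|---|---|---|---|---|
| 34% to 26% | 84.3% | 71.6% | 54.1% to 90.3% | 65.9% to 96.3% |
| 48% to 40% | 78.2% | 63.4% | 48.8% to 86.3% | 60.5% to 94.1% |
| 19.5% to 27.5% | 89.4% | 79.2% | 65.0% to 95.9% | 78.1% to 99.1% |

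The pooled column shows higher power, but only for the average of the two package effects.

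**The case against.** The best defence is that the two-level phrase is a drafting slip. No section says that the Enhanced arms will be combined. Section III.A promises change for each group, the baseline comparison in the analysis plan covers three groups, and Section V.C, item 5.A names two interventions. The sentence just before the fixed part refers to clustering by school, although the study samples kebeles and communities, so the paragraph fits this design poorly. The form asks only for a brief plan.

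Much of this stands. A reader might infer that the plan cannot give separate package effects at all. The documents do not support that: the GEE text speaks of a given intervention group against the control, which naturally allows one effect per package. The two outcomes used for sizing, poor or borderline food consumption and minimum dietary diversity, are binary and fall under that text. An example of averaging should therefore not be built on them.

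The defence does not remove the rest. Describing change within each group does not define a contrast between groups. A likely slip is still the only rule stated for the mixed model. And even the generous reading makes every comparison with the control, which leaves livelihoods against no livelihoods unspecified.

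**Conclusion.** The point holds for the mixed models of continuous outcomes. Taken literally, they return one averaged effect for two different packages and so cannot meet the study's aim. For binary outcomes the text is open but compatible with separate package-versus-Basic effects, so an outcome analysed both ways may be given two different comparisons. The contrast that isolates livelihoods is missing from both models.

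The averaging result rests on equal arms and equal retention. The 0.87 ratio rests on equal variance and clustering.

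A reader might also infer that the analysis mixes a randomised comparison with a non-randomised one. That would follow only if the arms are pooled and if Section II's account of assignment is the right one. Sections III.A and V.C, item 5.A give different accounts, so the documents do not settle it. For the same reason, Enhanced minus Basic cannot yet be labelled a randomised contrast. The inclusion criteria also differ by package (savings groups; plus Care Groups; plus a livelihoods pathway), which bears on how any of the contrasts is interpreted.

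**What to change.** 1. In Section V.C, item 3, replace the two-level group term with a three-level package factor (Basic as reference) and package-by-time terms (2 df), in both the mixed and the GEE models.
2. Name three contrasts in change: Enhanced minus Basic, Enhanced + Livelihoods minus Enhanced, and Enhanced + Livelihoods minus Basic.
3. State which contrast is primary, or how multiplicity is handled. One option is to test the 2-df package-by-time term first and then the pairwise contrasts. With exactly three groups this controls the familywise error rate without dividing alpha by three.
4. Reconcile Sections II, III.A and V.C, item 5.A on how packages and livelihoods were assigned. Only then say which contrasts, if any, are randomised.

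**Cost.** A few sentences and no new data, if settled before the endline analysis. Pairwise contrasts are less precise than a pooled one, and an adjustment such as alpha 0.05/3 would lower endline power for 8 points from 78.2%-89.4% to 63.4%-79.2%. That loss is the price of answering the question the study asks.

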*Excludes free zone kebeles (where intervention packages may change) and Ifaa Basic+Livelihoods kebeles; **one kebele excluded as a potential study location due to access concerns

As the Ifaa consortium learning partner, JHSPH has been requested to design an effectiveness evaluation of the different intervention packages to compare their outcomes in terms of key project indicators. The effectiveness evaluation will be independently designed and managed by JHSPH with the engagement of a private data collection firm.

III. Study Design:

A. Study Design Overview

This study will leverage randomization of the Ifaa Basic and Enhanced Interventions and partial coverage of livelihoods interventions to **compare the outcomes of three different intervention packages** as illustrated in Figure 1. As part of the cross-learning activity, 70 Kebeles will have enhanced interventions (including nutrition interventions such as Care Groups² and

² Care Groups, is a group of 10-15 volunteer, community health educators who regularly meet together with CRS project staff for training and supervision. Each of these volunteers then go out at least monthly to do health promotion with a small cohort of mothers of young children. Each volunteer is selected by the mothers she serves and is responsible for regularly visiting a relatively-fixed group of 10-15 of her neighbors each month, sharing what she has learned and facilitating behavior change at the household level.

[figure not shown]
CCFLS³), and of these 50% (n=35) will have enhanced livelihoods interventions (package varies by location) while half will not have livelihoods programming; a total of 50 Kebeles will have the only “basic” intervention package, and of these 50% (n=25) will randomly have the basic livelihoods intervention. Restricting the study to Kebeles that underwent randomization has methodological benefits as compared to a quasi-experimental design that would be required if the study was expanded to other project areas. An overview of the study flow is presented in **Figure 2**.

Figure 1. Ifaa Interventions and Study Groups

| | Ifaa Livelihoods Programming | |
|------------------------------------|------------------------------|----|
| | Yes | No |
| Ifaa Basic Intervention Package | not a study arm | X |
| Ifaa Enhanced Intervention Package | X | X |

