A. *If the study has different arms, explain the process for assigning participants (intervention/control, case/control), including the sequence and timing of the assignment.*

The selected sites will be purposively allocated to 1) the Ifaa basic package (comparison); 2) basic package + care groups (intervention 1); and 3) basic package + care groups + livelihoods (intervention 2) by CRS and other implementation partners in ifaa project. The JHU research team is not engaged to the assigning interventions.

Sections B thru F are not relevant.

VI. Data Custody, Management, Security, and Confidentiality Protections:

1. Data Sources: Identify the source(s) of data.

Participant/Parent-Guardian/Legally Authorized Representative
 JHM Medical Records (from Epic)

Note for JHM Data Users Only: Please complete the **Data Trust Risk Tiers Calculator** available on the Applications and Forms page on the JHSPH IRB website: [<https://tinyurl.com/2p96md3s>] and upload a copy of the documents to the "Miscellaneous- Other" section of your PHIRST application.

In addition, review the **Data Protection Attestation for Research and/or Healthcare Operations** at: [<https://tinyurl.com/yszfkur>] and certify your attestation of compliance to those requirements.

I certify my attestation of compliance to JHM Data Protection Requirements

Non-JHM Medical Records
 Outside Data Provider (CMS, National Death Index, Insurance Co., etc.)
 Other Existing Records (please specify):
 |
 |

2. Data Content: Will you collect, use, and/or record personal identifiers about study participants for any purpose?

Please look at the list of identifiers in Question 3 to help answer this question. **Note: Limited Data Sets (including dates, ages, and zip codes) are considered to be "identifiable".**

Yes: Continue with Question 3

| | | |
|--|-------------------------------------|---|
|  | No: Skip to Question 6 | |
| 3. Data Identification: Identify the Personally Identifiable Information (PII)/Protected Health Information (PHI) you will access/collect by checking the box(es) below for "Recruitment" and "Study Data" needs. | | |
| Recruitment | Study Data | PII/PHI to be Accessed/Collected |
|  |  | Name, signature, initials or other identifiable code |
|  |  | Geographic identifier (address, GPS location, etc.) |

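### The documents give three inconsistent accounts of how kebeles were assigned, and the analysis plan does not separate the livelihoods contrasts from the randomised one

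*Combined protocol and SAP*

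**What the plan says.** Three places describe assignment.

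- **Section II, text before Table 2:** "A subset of kebeles (n=70) was randomly allocated to Ifaa Basic and Ifaa Enhanced Packages"; and on livelihoods, "livelihoods kebeles were selected based on criteria developed by CRS, but assignment to the enhanced vs basic package was random".
- **Section III.A:** the study will "leverage randomization of the Ifaa Basic and Enhanced Interventions and partial coverage of livelihoods interventions". It states that "70 Kebeles will have enhanced interventions", 35 of them with livelihoods, and that "a total of 50 Kebeles will have the only" basic package, 25 of them given livelihoods at random. It presents the restriction to randomised kebeles as an advantage over a quasi-experimental design.
- **Section V.C item 5.A**, the template question on how arms are assigned: "The selected sites will be purposively allocated to 1) the Ifaa basic package (comparison" arm) and to both intervention arms, by CRS and its partners, without the evaluation team.

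Figure 1 leaves out the Basic + Livelihoods combination. Section III.A item (1) picks two kebeles per arm in each woreda, purposively, so that arms are alike in agro-ecological zone and remoteness. The same section adds that "if needed, adjusted models will be used to account for baseline differences between groups". Section IV.A sets a different planned participation for each arm: savings groups only; savings and Care Groups; or both plus a livelihoods pathway. The analysis plan (Section V.C, item 3) uses group, time and group-by-time throughout. It controls for individual or household characteristics that differ significantly at baseline.

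**The concern.** What was randomised decides which of the three pairwise contrasts can be read causally, and the reader cannot tell from the documents. The analysis plan gives all contrasts the same model and the same standing. If livelihoods kebeles were chosen on criteria related to how food security would have moved anyway, that movement would be credited to the livelihoods package. Section VIII.B says the findings will inform CRS programming and USAID funding calls, so an over-read livelihoods result would have consequences.

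**Working it through.** **1. The counts.** Section III.A: 70 + 50 = 120 kebeles. Table 2: 25 + 34 + 35 = 94 eligible. Adding the 25 Basic + Livelihoods kebeles and the "one kebele excluded as a potential study location due to access concerns" gives 94 + 25 + 1 = 120. The 25 comes from Section III.A itself, so this is not fully independent. A second check is: 241 project kebeles, about half in the free zone, leaves about 241 / 2 = 120.5. Enhanced alone is 34 + 35 = 69, or 70 if the excluded kebele was an Enhanced one, which the footnote does not say. So the 70 in Section II is probably the Enhanced total, not the number randomised to both packages.

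**2. The three accounts, side by side.**

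| Source | Enhanced vs Basic | Livelihoods |
|---|---|---|
| Section II | random | chosen on CRS criteria |
| Section III.A | random | random among Basic kebeles; not stated for Enhanced |
| Section V.C item 5.A | purposive | purposive |

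The random element in Section III.A concerns Basic kebeles, whose livelihoods half is not a study arm. It does not show that livelihoods was random among Enhanced kebeles.

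**3. Which contrasts carry the selection, taking Section II as true.** Basic and Enhanced are both without livelihoods; Enhanced + Livelihoods is with. Livelihoods status therefore differs in both contrasts that involve the third arm, and no retained arm separates package from kebele selection. Planned enrolment in a livelihoods pathway (Section IV.A) adds selection at household level.

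**4. What group-by-time removes.** Let D be an arm's mean two-year change had the packages made no difference. The interaction estimates: true effect + (D in Enhanced + Livelihoods − D in comparator). Stable level differences cancel; a difference in D does not.

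**5. What a main-effect covariate adds.** With complete two-wave data, the linear interaction estimate is the difference between arms in mean (endline − baseline). A covariate fixed over time is subtracted from itself, so the estimate is unchanged. For the logit model this is not exact. A simulation checked it on assumed values: no true effect; a kebele factor 1 SD higher in the livelihoods arm, shifting change by −0.3 log-odds per SD; 3 arms × 16 kebeles × 60 households; 500 data sets per setting. Mean interaction estimates were −0.18 to −0.29 unadjusted, −0.20 to −0.29 with the factor as a main effect, and −0.01 to +0.02 with factor-by-time added. The −0.3 was put in, so only the pattern is informative.

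**6. What an assumed trend difference would do to the test.** From Section III.B: 1,080 × 0.8 / 1.5 = 576 effective households per arm. SE of the difference in change = √[4p(1 − p)(1 − ρ)/576], with within-household correlation ρ assumed to be 0 to 0.5. This gives 2.9 to 4.2 points at p = 48% and 2.8 to 4.0 at p = 34%. With no true effect, a nominal two-sided 5% test rejects in 8–11% of trials if trends differ by 2 points. If they differ by 4 points, it rejects in 16–27% (48% baseline) or 17–30% (34%). The 2 and 4 points are assumptions.

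**7. Whether woreda-by-time would help.** Under Section III.A, each arm has 1,080 / 9 = 120 households per woreda. With equal arm sizes within woreda, the overall difference in change equals the average of the within-woreda differences. Woreda terms therefore leave the linear estimate, and any bias in it, where it was. Unequal loss or a logit link makes this approximate.

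**The case against.** The purposive wording in Section V.C item 5.A may be loose language for the purposive choice of study kebeles in Section III.A item (1); the phrase about selected sites may simply mean the study sites. Section III.A already distinguishes randomisation of packages from partial coverage of livelihoods, picks kebeles that are alike in zone and remoteness, and provides for adjusted models. The analysis plan collects residence location for possible control, models change, and is a brief plan by the template's own description.

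Much of this stands. The loose-wording reading is plausible, but the text does not say so, and item 5.A is the formal answer on assignment. The matching covers two named factors, not the unstated CRS criteria. The adjusted models are conditional and directed at baseline differences, whereas the exposure here is to differing trends. The distinction drawn in the design section is not carried into the analysis.

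A reader might go further and infer that nothing was randomised, or that the livelihoods result is known to be biased. The documents support neither. Sections II and III.A both state that packages were randomised, and nothing shows how the CRS criteria relate to change in the outcomes. Nor does the 70 against 120 show a failed randomisation; it looks like a slip in the text.

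**Conclusion.** The concern holds. Assignment is described in three inconsistent ways, with two different counts. On the Section II account, both Enhanced + Livelihoods contrasts are non-randomised and open to confounding of two-year change, and the planned adjustment rule does not address it. Enhanced versus Basic, both without livelihoods, then rests on randomisation, subject to the purposive choice of kebeles and the arm-specific eligibility.

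The bias may be nil or material, in either direction: the CRS criteria and the kebele trends are not given. The rejection rates and simulated estimates above rest on assumed values and are not estimates for this trial. The conclusion about the livelihoods contrasts is conditional on Section II. It would change if livelihoods among Enhanced kebeles proved to have been random, and it would widen to all contrasts if Section V.C item 5.A is literally right.

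**What to change.** Before the endline analysis:

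1. Reconcile Sections II, III.A (including kebele selection) and V.C item 5.A to one account of what was randomised, by whom and when, and correct the 70 or 120.
2. Label the contrasts to match.
   - If Section II is confirmed, present Enhanced versus Basic as randomised, with the two caveats above, and both Enhanced + Livelihoods contrasts as non-randomised with limited causal claims.
   - If Section V.C item 5.A is literally right, label no contrast as randomised.
   - If livelihoods among Enhanced kebeles is shown to have been random, label those contrasts accordingly.
3. For non-randomised contrasts, obtain the CRS selection criteria and pre-specify them, with agro-ecological zone and remoteness, as kebele-level factor-by-time terms whatever the baseline p-values. Where arms do not overlap on a criterion, report that and do not extrapolate.

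Woreda-by-time may be added because sampling is stratified by woreda. It serves precision and is not a remedy for this bias.

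The cost is protocol and analysis wording and one request to CRS, with no change to sites or data collection. Only measured factors are controlled, and the livelihoods claim becomes more modest. Degrees of freedom are limited. Two kebeles per arm in eight woredas (those listed in Table 2) or nine (Section III.A) gives 32 to 36 kebeles per two-arm contrast, more if small kebeles are topped up. Zone and a two-level remoteness factor (assumed) use 2 + 1 = 3 terms, the CRS criteria an unknown number, and woreda 7 or 8 if added.
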